# 7.2 Follow-up Phase:

# 7.2.1. The main study:

The ILR devices will be implanted over the course of 12-24 months (1-8 implantations per week in each of the centres), starting at the beginning of 2014.

• Participants in the ILR group will be seen at in-hospital visits at 12, 24 and 36 months after ILR implantation. Between in-hospital visits they will be followed by daily automatic ILR remote telemedicine transmissions. Data from the ILRs are automatically transmitted to a central database. Every day, an experienced medical doctor reviews the recent transmissions in the database. Subjects will be contacted if transmissions are not received in a period of 14 days, and any system malfunctions will be corrected. If a new-onset AF episode lasting minimum 6

minutes is detected, two senior cardiologists independently evaluate the transmission. In case of disagreement, a third senior cardiologist will independently evaluate the episode. If the two or two of three cardiologists confirm the diagnosis of AF, OAC will be initiated by the local center (see section 7.8), and this will be registered in the eCRF. Remote monitoring will continue until the end of battery life, study withdrawal, or death occurs. At in-hospital visits, QoL and MoCA forms will be filled. Adverse events will be collected at study visits and by lookup in medical records and registries at least on a yearly basis until the end of study.

Participants in the control group will be seen only at inclusion and after the 3 year follow-up.
 During this period they will be seen by their general practitioner. Between the scheduled visits
 QoL forms will be sent by mail. MoCA forms will be filled in on the final follow-up. Adverse events will be collected at study visits and by lookup in medical records and registries at least on a yearly basis until the end of study.

Additional visits are made at the discretion of the caring physician. Throughout the study the investigator or study nurse/coordinator should continue to provide appropriate medical care.

The following assessments and procedures will be performed at specified time points during the study and will be recorded in the eCRFs (for details please see Appendix A, section a and b):

- CHADS-VASc score: At randomization.
- Blood sample: At randomization. Some participants might have additional blood samples taken.
- NYHA functional classifications: At randomization and (12, 24,) 36months.

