# 7.2.1 The ECG study:

The ECG computer analysis study will collect periodic data from the ILR during sinus rhythm and during episodes of AF (both patient-activated and automatic sampling). Patients in the ILR group will be encouraged to make a monthly patient-activated sampling after five minutes of rest (most likely in sinus rhythm). Standard 12-lead ECGs will be obtained at baseline (ILR and control groups) and also annually in the ILR group. ECG markers predictive of future AF will be derived from the recordings. Objectives:

Primary: To study the the association between chronological developments of ECG markers measured by ILRs and incident AF, in order to identify which patients fall into low or high risk AF groups.

Secondary: Calculation of daily AF burden (ILR group) to refine quantification of episodes beyond merely presence/absence and to guide decisions regarding the need for anticoagulation. Relationship between AF burden and development of ECG markers.

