#### Comments:

Individual personal data on resource use and health outcomes will be collected prospectively during the trial or from national registers, which also continuously record healthcare consumption. The framework for the analysis is a cost-utility analysis where the mean differences in costs and QALYs between the intervention and the control group is expressed as a ratio that shows the cost per QALY gained from the introduction of ILR monitoring and subsequently AF management. All costs will be estimated from a societal perspective.

Resource use data in relation to the implantation of ILR, ILR data transmission and analysis, as well as follow-up visits, will be recorded prospectively. The registration will include noting the amount of time staff spend during pre-operative evaluation, procedures (e.g. blood tests, electrocardiogram), utensils, anaesthetics, sedatives, antibiotics and hospital stay for each participant. In order to estimate costs, information about salaries, the cost of utensils, pharmaceuticals and equipment will be collected from the hospital finance department.

Data on the participants' use of inpatient and outpatient hospital care and use of emergency departments, general practitioners and other private practising medical specialists, physiotherapists, chiropractors, chiropodists and psychological counsellors, as well as prescription drugs, will be collected from the National Patient Register, the National Insurance Service Register, and the Register of Medicinal Product Statistics. It is assumed that costs of healthcare consumption unaffected by the intervention will cancel out due to randomization. Furthermore, it is assumed that all AF management costs will be captured in the register data.

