Descriptive analyses will be used to describe the mean QALYs, resource use and costs per participant in both arms of the trial. Differences in QALYs, resource use and costs between the two groups after 24 months of the study will be based on the trial data. Confidence intervals of 95% for differences between the two groups will be computed based on bootstrap re-sampling with 5,000 replications of the trial data.

For the cost-effectiveness analyses, the incremental cost-effectiveness ration (ICER) will be estimated on the basis of the mean difference in costs relative to the mean difference in

QALYs. Uncertainty about the ICERs will be analysed using bootstrapping and presented in a cost-effectiveness plane. A cost-effectiveness acceptability curve will be generated to represent the probability that ILRs are cost-effective compared with usual treatment. Estimates of the costs per QALY gained from ILR will be compared to similar estimates of rehabilitation after stroke, AF management as well as other cost-effectiveness estimates in other treatment areas.

Study nurses will register all contacts between study subject and study nurse in the hospital files to be included in the cost evaluation.

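### The cost evaluation counts follow-up visits and all study-nurse contacts without separating research data collection from ILR care, and the visit schedule places more of these in the ILR arm

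*Protocol*

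**What the plan says.** Section 7.2.2 (health economic study) defines the result as a cost-utility ratio: the difference in mean costs over the difference in mean QALYs, read as the cost per QALY of introducing ILR monitoring and the AF management that follows. Group differences are taken after 24 months.

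Two sentences there decide which contacts are costed. The first covers device-related use and visits: "Resource use data in relation to the implantation of ILR, ILR data transmission and analysis, as well as follow-up visits, will be recorded prospectively". The second covers nurses: "Study nurses will register all contacts between study subject and study nurse in the hospital files to be included in the cost evaluation". Neither separates contacts by purpose.

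The visit schedule is in section 7.2.1 (main study). For the ILR arm: "Participants in the ILR group will be seen at in-hospital visits at 12, 24 and 36 months after ILR implantation". For controls: "Participants in the control group will be seen only at inclusion and after the 3 year follow-up"; between these two visits, "QoL forms will be sent by mail". On what is done when ILR subjects attend, the section says "At in-hospital visits, QoL and MoCA forms will be filled". The ECG study adds "Standard 12-lead ECGs will be obtained at baseline (ILR and control groups) and also annually in the ILR group".

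**The concern.** A cost per QALY for adopting ILR screening should contain what a health service would spend on the screening: implantation, remote monitoring, handling of transmissions and complications, and treatment of detected AF. It should not contain what the trial spends on measuring its own endpoints.

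If research contacts were equally frequent in both arms, they would largely cancel in the difference. Here the schedule is unequal, and the comparison is made before the control arm's only follow-up visit. The one cancelling assumption in section 7.2.2 is limited to health care use that the intervention does not affect, so it does not reach visits scheduled in one arm only.

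At stake is one of the three results promised under Expected results, which is meant to inform health policy decisions. The primary endpoint is not affected.

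**Working it through.** The protocol states no cost, QALY or ICER figure for the comparison, so there is none to reproduce. The check is a count of scheduled visits and a comparison of passages.

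**1. Scheduled hospital visits after inclusion and, in the ILR arm, after implantation** (section 7.2.1, main study)

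| Up to | ILR | Control | Difference |
|---|---|---|---|
| 24 months, nominal | 2 (months 12, 24) | 0 | 2 |
| 36 months, nominal | 3 (months 12, 24, 36) | 1 | 2 |

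**2. Is the second ILR visit inside the 24-month window?** Appendix A puts implantation on day 14 and the visits on days 374, 734 and 1094.
- Counted from implantation: 734 − 14 = 720 days = 24 × 30, which is exactly 24 months in the chart's 30-day months.
- Counted from randomization: 2 × 365 = 730 days, so day 734 is 4 days too late. The chart itself labels the visit month 24.5.

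Section 7.2.2 does not say from which date its 24 months run. The count is therefore one visit per ILR subject, or two if day 734 is included, against none in controls.

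**3. What the visits contain.** Appendix A, months 12.5 and 24.5, leaving aside optional items:

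| Item | ILR | Control |
|---|---|---|
| Medical history, concomitant disease and medication | yes | yes |
| QoL and cognitive function | yes | yes |
| Adverse events, health economics | yes | yes |
| 12-lead ECG | yes | no |
| Vital signs | yes | no |
| Remote ILR interrogation | yes | no |

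The only item specific to the device is remote interrogation, and section 7.2.1 says transmissions are automatic and daily. Most of the rest is trial measurement. It is not all research, however: section 10.6.2.3 has ILR complications asked about at every visit.

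**4. The control column.** Appendix A ticks several items for controls at months 12.5 and 24.5, while section 7.2.1 allows no control visit then and places their follow-up MoCA at the final visit. Mailed forms and register look-up would explain most of the ticks, but the protocol does not say so. The count of zero rests on section 7.2.1.

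**5. Effect on the ratio.** Let *k* be the scheduled visits in the window (1 or 2 for ILR, 0 for control), *s* the share of a visit that is research only, *c* the cost of a visit, and *n* the between-arm difference in the cost of other research-only nurse contacts.

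- Excess in incremental cost per subject = *k* × *s* × *c* + *n*
- Shift in cost per QALY = (*k* × *s* × *c* + *n*) / ΔQALY

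Only *k* can be read from the protocol. The visit term is positive whenever *s* and *c* are. With a positive ΔQALY it moves the ratio upwards, against ILR. No DKK figure follows without inventing *s*, *c*, *n* and ΔQALY.

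**The case against.** The strongest reply is that these visits are part of ILR follow-up. Section 7.2.1 describes remote transmission as what happens between hospital visits, section 7.2.2 lists follow-up visits beside implantation and transmission, and complications are sought at each visit. Some nurse contacts plainly belong to the intervention: telephone help with transmissions (section 7.5) and calls after 14 days without data (section 7.2.1). All of this stands. A reader might infer that the visits are trial-only, but the documents show mixed visits, so removing them whole would bias the ratio the other way.

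A reader might also infer that nurse contacts are charged to the ILR arm alone. The text does not say that. Contacts are registered for study subjects in general, and costs are described for both arms. The imbalance comes from the schedule.

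A third inference is double counting, since register data are used too: "Data on the participants' use of inpatient and outpatient hospital care and use of emergency departments". The protocol does not show whether study visits or study-funded implantations produce register entries, and removing overlap between sources is ordinary analysis-plan detail. It is no finding here.

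It can also be said that a health-economic analysis plan may settle the matter. But the protocol states an inclusion rule for all nurse contacts, so this is more than silence, and the purpose of a contact is hard to reconstruct unless it is noted at the time. The societal perspective does not answer the point either: it widens whose costs count, without making trial measurement part of screening.

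**Conclusion.** The concern holds in a limited form. Followed as written, section 7.2.2 carries research-driven costs into the comparison, and the schedule puts more of them in the ILR arm: one or two scheduled visits per subject by 24 months against none. The bias from these visits has one direction, towards a higher incremental cost and, with a positive QALY gain, a higher cost per QALY for ILR.

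Its size is unknown. A reader might want to express it as a share of the device price or of the stroke costs avoided. That would need an assumed visit cost, and neither comparison is the ICER, which also contains implantation, transmission review and anticoagulation. The documents support the direction and the visit count, and no figure beyond these.

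The conclusion rests on two readings: that controls have no visit before 3 years, as section 7.2.1 states despite the Appendix A ticks, and that at least part of each ILR visit serves trial measurement only. The consequence is confined to the health-economic result, but the correction is cheap and worth making.

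**What to change.** In section 7.2.2:

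- Record the purpose of every visit and study-nurse contact, in both arms, when it occurs.
- In the base case, exclude contacts, or the part of a visit, made only to collect trial data (for example QoL and MoCA forms or the ECG-study recording).
- Keep contacts caused by the device, its transmissions, complications or detected AF.
- Report the result with all contacts included as a sensitivity analysis.
- State the date from which the 24 months run, so that it is clear whether the visit on day 734 counts.

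Reconcile the control-arm ticks in Appendix A at months 12.5 and 24.5 with section 7.2.1, saying which items are obtained by mail or register.

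The cost is one field on the contact record and a few sentences of text. The downside is some judgement in dividing mixed-purpose visits; the sensitivity analysis shows how much depends on it.

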# 7.2.3 The MRI study:

Patients with risk factors for stroke frequently have asymptomatic previous brain infarcts.  Age, hypertension and diabetes predispose to white matter hyperintensities, which is associated with cognitive disorders, balance and mood disorders.  In a subset of the study participants (approximately 500 subjects) we will perform MRI of the brain upon study entry to detect previous brain infarcts (semi-quantitative assessment) and white matter hyperintensities (semi-quantitative assessment). MRI scans will be performed without contrast injection. In the patients in whom stroke occurs during follow-up a second MRI should be performed close to the time of stroke. In the subjects who had a first MRI scan performed a final MRI should be performed at the end of the study. MRI scans of brain are performed with 3 sequences: FLAIR, DWI and Gradient Echo sequencing. In a subset of participants we will perform an MRI scan of the heart with Gadolinium contrast to measure chamber dimensions, wall-motion and late enhancement (fibrosis) (approximately 200 subjects).

# 7.3 Endpoint Determination:

# 7.3.1 Definition of Endpoints:

Please see Section 10. Details are provided in Appendix F.

#### 7.3.2 Data Collection:

Endpoint data will be collected on specific eCRFs. For all possible primary endpoints, and all deaths, all supporting documentation from medical records, imaging, laboratory tests, registries, etc., will be collected, and will be provided to the EC during the course of the trial for review and confirmation of events as outlined in the EC charter.

# 7.4 Genetic analysis and Biomarkers:

At randomization 3 types of blood vials will be collected (whole blood sample, EDTA while sample, and serum sample). Please see Appendix D for handling of blood samples. Blood samples will be used for genetic and biochemical analyses.

Other markers will be acquired as described above: ECG, and MoCA test (and imaging in a subset of patients).

# 7.5 Strategy for management of low inclusion rate:

- 1) Too low patient recruitment due to healthcare professionals or logistics: We will continuously monitor patient inclusion each month per centre. If a centre does not recruit the expected number of patients we will recruit a new centre. In the interim period the other centres will increase their recruitment.
- 2) Too low patient recruitment due to patient preferences: We conducted a small survey asking potential candidates if they would participate if asked, and patients were positive. A logbook will be used to list and identify reasons why patients decline to participate. If better information can increase the participation rate we will improve the quality of the information. Otherwise additional letters of invitation will be sent.
- 3) Patients cannot perform telemedicine transmissions: Rigshospitalet is currently performing another study with ILRs in elderly patients with valve disease (aortic stenosis). These patients are fully capable of performing telemedicine transmissions. In the event of problems, study nurses will guide the patients by telephone.

# 7.6 Study guidelines dealing with definition of AF:

Arrhythmia which the device has sampled and categorised as AF and which is afterwards:

- confirmed as AF by a study investigator and
- has a duration of ≥ 2 minutes (please note that this is not the same as AF which requires anticoagulation therapy)

After new AF has been diagnosed the patient will continue unaltered arrhythmia monitoring as previously performed. The device requires 2 minutes for AF detection.

#### 7.7 Study guidelines how to treat AF detected by ILR:

When AF is detected by the ILR and the episode is verified by an investigator and has a qualifying duration (i.e. an episode which has a duration ≥ 6 minutes), the patient is given advice to start therapy with one of the newer OAC (preferred strategy) or conventional OAC according to local routine. It is recorded if the patient actually will receive OAC. Subjects will be covered by normal patient insurance.

# 7.8 Study guidelines how to treat AF detected by other methods (also relevant for the control group):

When AF is diagnosed in the control group or in the ILR group by non-ILR methods (including monitoring during hospitalisations, Holter, ECG, etc) patients are recommended to start anticoagulation according to the same guidelines as mentioned in the section above (section 7.8).

#### 8. REMOVAL AND REPLACEMENT OF SUBJECTS:

#### 8.1 Removal of Subjects:

A subject has the right to withdraw from the study at any time, for any reason, without prejudice to his or her future medical care by the physician or at the institution. Any subjects who withdraws consent to participate in the study will immediately be removed from further treatment and/or study observations on the date of request. The investigator has the right to withdraw the subject from the study, if any of the following occurs:

- Significant illness caused by the ILR
- Refusal by the subject to continue observations
- Decision by the investigator, that termination is in the subjects best medical interest
- Loss to follow-up

Should a subject (or legally acceptable representative) request or decide to withdraw from the study, all efforts will be made to complete and report the observations as thoroughly as possible up to the date of withdrawal. All information should be reported on the applicable eCRF. A complete, final evaluation and assessment (section 7.4) should be made at the time of the subject's withdrawal. The end of study eCRF will be completed with an explanation for the withdrawal. If the withdrawal of a subject is due to an AE, follow-up visits should be scheduled until the AE has resolved or stabilized. Unless consent has been withdrawn, follow-up date on death and hospitalizations will be collected until study termination, though if specifically requested by the patient, the patient will not be followed for the primary endpoint until end of study.

# 8.2 Replacement of Subjects:

Randomized subjects will not be replaced if discontinued.

#### 9. ADVERSE EVENT REPORTING:

#### 9.1 Definitions:

#### 9.1.1 Adverse Events:

An AE is defined as stroke (hemorrhagic or ischemic), peripheral emboli, bleeding, cardiac event (atrial fibrillation, ventricular or supraventricular tachyarrhythmias, bradycardia, pacemaker implantation, myocardial infarction, unstable angina, percutaneous coronary intervention, coronary artery bypass graft or heart failure) or ILR infection, occurring in a subject after the initiation of the study, whether or not considered to be related to the implantation of the ILR. Elective hospitalizations (i.e., due to any pre-existing systemic illness or elective surgery) are not AEs. Abnormal laboratory values should not be reported as AEs, unless they fulfil the definition above.

#### 9.1.2 Serious Adverse Events:

A serious adverse event is defined by regulatory agencies as an AE that poses a significant hazard or side effect, regardless of the investigators or sponsors opinion on its relationship to the investigational product. This includes, but may not be limited to, any event, that:

- Is fatal, or
- Is life threatening (places the subject at immediate risk of death), or
- Requires in-patient hospitalization or prolongation of existing hospitalization, or
- Leads to persistent or significant disability/incapacity

A hospitalization meeting the regulatory requirement for "serious" criteria is any in-patient hospital admission, which includes a minimum of an overnight stay in a health care facility. Any event, that does not exactly meet this definition, which in the investigators opinion represents a significant hazard, can be assigned "other significant hazard" regulatory reporting serious criteria. Additionally, important medical events that may not be immediately life-threatening or result in death or hospitalization, but which may jeopardize a subject or require intervention to prevent the outcomes listed above, or result in urgent investigation, may be considered serious. Examples include allergic bronchospasm, convulsions or blood dyscrasia. Serious Adverse Events will be reported based on patients information to study personal or monthly registry retrievals and will be filed in CRFs by the local study team.

# 9.2 Reporting Procedures for All Adverse Events:

All AEs occurring after randomization observed by the investigator or reported by the subject (whether or not attributed to the investigational product), will be reported on the electronic case report form. The following

attributes must be assigned by the investigator:

- Diagnosis.
- Description: E.g. hospital records.
- Dates of onset and resolution and action taking.

The investigator may be asked to provide follow-up information. All AEs, serious or not, that result in a subjects permanent withdrawal from the study must be reported in the CRF. The end-of-study eCRF will be completed, giving details of the withdrawal.

Medically significant AEs considered related to the investigational product by the investigator or the sponsor will be followed until resolved or considered stable.

All deaths occurring in study must be recorded, and cause of death must be investigated. This includes deaths until determination of the study or a maximum of 60 months since enrolment of the subject, whichever is earlier.

It will be left to an investigators clinical judgement as to whether or not an AE is of sufficient severity to require a subjects removal from treatment.

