#### Enrolment

A subject is considered enrolled once the subject is randomized and the ILR implantation (or control) has been performed.

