#### 10.3 Sample Size Considerations:

We expect that 30% of the participants will have documented AF episodes lasting ≥6 minutes (and per protocol qualifying for OAC) during ILR monitoring for at least three years. The study population is expected to have a stroke rate of 0.7%/year in non-AF patients, and 2%/year in AF patients not treated with OAC. While we expect the number of AF-related strokes to be reduced by OAC, we assume that strokes unrelated to AF will not be influenced by this. We also include the assumption that 3% of all participants in the control group will become diagnosed with AF and start OAC. The annual rate of the primary end point in the control group is thus expected to be 1%. Finally, we expect that 5% in the ILR group will not be monitored due to refusal of ILR implantation or ILR explantation due to discomfort. These patients will participate at the same risk as patients in the control group and will be included in the analysis of the primary endpoint according to the intention-to-treat principle. We thus expect the overall hazard ratio to be 0.65. To analyse this reduction in the primary endpoint with a 2-sided α-level of 0.05 and a power of 80% in a 1:3 intervention:control-randomized population, we will need 279 primary events. Follow-up duration will be adjusted to accommodate the number of primary events. With an assumed length of inclusion period of 1-2 years and a median follow-up up 4 years, 6000 subjects will be needed.

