# 10.6.2 Analysis of Key Study Endpoints:

# 10.6.2.1 Primary Endpoint:

The principle analysis for the primary endpoints will employ the intend-to-treat principle, and use a survival analysis. To account for the competing risk of death, the cumulative incidences of the primary endpoint will estimated, plotted and group-wise compared in a multi-state fashion. A co-variate adjusted analysis of the combined primary endpoint using a cause-specific Cox proportional regression model will be performed as a supportive analysis. The hazard ratios and the corresponding 95% confidence intervals will be estimated. Subjects completing the study and not reaching the composite endpoint will be censored.

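### Section 9.2 stops recording deaths at 60 months per subject, in conflict with section 8.1 and the event-driven follow-up in section 10.3; late deaths are lost if the trial runs to 279 events

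*Protocol*

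**What the plan says.** Section 9.2 requires all deaths to be recorded and their cause investigated, then sets the window as the end of the study or "a maximum of 60 months since enrolment of the subject, whichever is earlier".

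Other sections set a different end or none:

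- Section 8.1, on removal of subjects, says that unless consent is withdrawn "follow-up date on death and hospitalizations will be collected until study termination".
- Section 10.3 makes the trial event-driven: "we will need 279 primary events. Follow-up duration will be adjusted to accommodate the number of primary events". No per-subject limit is stated for strokes or systemic embolism.
- Section 7.2.1 collects adverse events in both arms from visits, records and registries, at least yearly, until the study ends.
- Section 10.1 expects the study to conclude at 279 strokes or once 6,000 subjects have at least 36 months, about five years after the first enrolment. Section 3.5 lets the steering committee extend follow-up, or alter the sample size so as to finish in about five years. The synopsis also gives about five years in total.

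Death enters the analysis in three ways. In section 10.6.2.1 it is the competing event: "To account for the competing risk of death, the cumulative incidences of the primary endpoint will estimated". In section 10.2.2 all-cause death and cardiovascular death are secondary endpoints, and cardiovascular death is part of the first-listed composite. In the endpoint committee charter, a death adjudicated as caused by stroke is registered as a primary endpoint.

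**The concern.** The protocol gives two end dates for death follow-up, and the one in section 9.2 can fall before the end of stroke follow-up. Section 9.2 is also the sentence that sets a death-recording window for all subjects, whereas section 8.1 speaks of those who leave the study.

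A site following section 9.2 could stop recording deaths at month 60 while strokes still counted towards the 279. The mortality endpoints and the secondary composite would then lose their late events, and a stroke that came to light only through review of a death could be missed. Section 10.6.2.2 places the first two secondary endpoints, the composite and all-cause death, under Hochberg control, so the loss would touch the secondary results with formal error control.

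**Working it through.** **Inputs.** From the synopsis and section 10.3: 4,500 control and 1,500 ILR subjects; control rate 1% per year; hazard ratio 0.65, so 0.65% per year in the ILR arm; accrual of 1–2 years; 279 events; and the design "with a 2-sided α-level of 0.05 and a power of 80% in a 1:3 intervention:control-randomized population". The protocol gives no mortality rate, so 0–4% per year, equal in both arms, is an assumption.

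**Step 1: the 279.** Freedman's formula for unequal allocation, with k = 1/3 (ILR to control):

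(1.960 + 0.842)² × (1 + k × 0.65)² / [k × (1 − 0.65)²] = 7.849 × 1.4803 / 0.04083 = 284.5, so 285.

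This is within about 2% of 279. Schoenfeld's formula gives 226. The protocol's 279 is used below because it is the stated target.

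**Step 2: follow-up needed, ignoring attrition.** Events per year = 4,500 × 0.01 + 1,500 × 0.0065 = 54.75. Mean follow-up = 279 / 54.75 = 5.10 years, or 61.2 months. The mean alone passes 60 months. The median of 4 years stated in section 10.3 would give only about 4 × 54.75 = 219 events.

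**Step 3: calendar time to 279.** Entry is uniform over A years, the event hazard in arm g is λ, and the death hazard is μ. Expected first events by time T after first randomisation:

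E(T) = Σ n × mean over entry times e of { λ/(λ+μ) × [1 − exp(−(λ+μ)(T − e))] }

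Solve E(T) = 279. The share with potential follow-up beyond 60 months is (T − 5)/A, at most 1. All deaths are 6,000 × mean[1 − exp(−μ(T − e))]; those after the cap are this figure less the same expression with T − e limited to 5 years. Results for two-year accrual, with shares taken from unrounded T:

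| Mortality per year | T (years) | Subjects past 60 months | Deaths after cap / all deaths |
|---|---|---|---|
| 0% | 6.22 | 61% | – |
| 2% | 6.53 | 76% | 62 / 627 (10%) |
| 4% | 6.88 | 94% | 169 / 1,256 (13%) |

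With one-year accrual T is 5.72 to 6.37 years, so the cap still binds.

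**Step 4: favourable readings.** The component rates give 0.30 × 2% + 0.70 × 0.7% = 1.09% per year before any control-arm anticoagulation. With 1.09% in control (and the same hazard ratio), or 1% in both arms pooled, and no deaths, the 279th event still comes when the first subject is at 63–70 months, and 26–40% of subjects pass 60 months.

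**Step 5: the five-year end.** Two years of accrual plus 36 months puts the first subject at exactly 60 months, so the cap excludes nobody. E(5) is then about 215 events with no deaths and about 198 at 4% mortality, short of 279.

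**Step 6: effect on the stroke analysis.** In 400 simulated trials of the two-year accrual model, deaths after month 60 were left unrecorded and those subjects were kept at risk to study end.

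| Mortality per year | Mean hazard ratio, complete / capped | Control cumulative incidence at 6.2 years, complete / capped |
|---|---|---|
| 2% | 0.6539 / 0.6539 | 5.677% / 5.677% |
| 4% | 0.6559 / 0.6558 | 5.340% / 5.340% |

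No single trial's hazard ratio moved by as much as 0.002. This is expected: under administrative censoring the overall survival term and the risk set are inflated by the same factor, which cancels in the cumulative-incidence estimator. The simulation does not cover fatal strokes that are found only through a death.

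**The case against.** The strongest reply is that section 9.2 contains a stray clause in the adverse-event chapter which the rest of the protocol overrides. Four stronger readings are tempting, and the documents do not support them.

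- *That follow-up must exceed 60 months.* Sections 10.1 and 3.5 and the synopsis allow an end about five years after the first enrolment, or a larger sample. At that end the cap does not bind. This stands, although on the plan's own rates that end gives about 198–215 events. The gap between target and timeline is a separate sample-size matter.
- *That late deaths will certainly be lost.* Section 7.2.1 collects adverse events to the end of the study, section 7.3.2 and the charter send all deaths to the committee, section 8.1 collects deaths to study termination, and section 10.2.5 uses all available follow-up. In practice deaths may well be captured. What remains is that section 9.2 says otherwise.
- *That the competing-risk analysis of stroke is corrupted.* No section says that a subject with an unrecorded death stays in the risk set, and Step 6 shows almost no change if that happened. Estimates up to month 60 are unaffected in any case.
- *That the starting point of the clock biases the arms.* Enrolment is defined so that "A subject is considered enrolled once the subject is randomized and the ILR implantation (or control) has been performed". Section 6 plans implantation within four weeks, which is trivial against 60 months. Read literally, a subject who refuses the device never starts the clock and so is not capped at all.

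It can also be argued that a cap equal in both arms amounts to administrative censoring of the mortality endpoints, costing precision without introducing bias. That is fair for all-cause and cardiovascular death. It does not cover a fatal stroke known only from the death review.

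**Conclusion.** The point holds as an internal contradiction with a conditional loss of data. Section 9.2 cannot be reconciled with section 8.1, or with section 10.3 where "Follow-up duration will be adjusted to accommodate the number of primary events".

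The size given in Step 3 rests on running to 279 events with 6,000 subjects at the stated rates and two-year accrual. The share of deaths lost further rests on an assumed mortality of 2–4% per year. The loss falls on all-cause death, cardiovascular death and the secondary composite, together with any primary event identified only by adjudicating a death. The main stroke comparison is otherwise hardly touched. The protocol should be corrected because the rule is explicit and the event target it conflicts with is the trial's own, but the conflict does not threaten the validity of the principal analysis.

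**What to change.** Delete the 60-month limit in section 9.2. State that deaths are collected for every randomised subject, from randomisation to the same end-of-study date as the primary endpoint, unless consent is withdrawn, in line with section 8.1. Counting from randomisation also removes any question about when enrolment occurs.

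The cost is one sentence. The registry and record lookups that section 7.2.1 already plans at least yearly, to the end of the study, can supply the deaths. The additional work is committee review of the late deaths.
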